The StepRite system developed by MedHab (<http://www.medhab.com/>) allows the physical therapist to monitor physical activity and exercise remotely, thereby reducing the need for frequent out-patient visits. A thin insole placed inside the shoe measures foot contact pressure and acceleration. This information is translated into quantitative feedback about exercise compliance and performance measures comparing the surgical side with the non-surgical side. Real time feedback during exercise and weight-bearing activities is

provided to the patient, and a HIPAA secured user interface website also displays this information in an online dashboard for both physical therapists and the physician.

With the advent of federally mandated bundled payments for total joint replacement, active management of the rehabilitative process postoperatively with quantifiable data will be necessary to ensure financial stability.

Given the potential for improving patient engagement with rehabilitation, this study proposes a treatment model which includes monitoring activity outside of the clinic using the StepRite device and using a combination of outpatient appointments and remote consultations with therapists.

Significance of this study

The significance of the proposed study includes the projected benefit to the patients in terms of attaining clinical outcomes quicker and to the medical system in terms of managing cost for the provision of services. Subjects are expected to demonstrate improved compliance to patient tailored rehabilitation protocols which will lead to more rapid attainment of clinical outcomes versus present traditional rehabilitation methodologies. The expected level of, and rate of, attainment of clinical outcomes will translate to an overall reduction of cost to the medical system by reducing the need to engage in additional processes or the need to protract the time required to attain clinical outcomes, where either or both in combination can increase rehabilitation expenditures.

Objectives

To compare the efficacy of StepRite in a prescribed physical therapy program verses traditional in-facility physical therapy program after partial or primary total knee replacement using validated survey tools to evaluate patient progress, including patient self-reporting of progress and surgeon appraisal of patient performance post-operatively.

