To compare the overall cost of post-operative rehabilitation of patients involved in traditionally employed regimens versus those using the StepRite device.

Hypothesis and specific aims

The aim of this study is to evaluate whether improved clinical outcomes as well as reduction in cost in provision of care can be better affected through the use of the Steprite device as compared to the use of traditional rehabilitation modalities.

We will seek to reject the null hypotheses that 1) there is no difference between clinical outcomes attained between patients using the Steprite device and those using traditional rehabilitation modalities and that 2) there is no reduction in cost to the medical system when patients use Steprite versus other conventional methods of rehabilitation.

By rejecting the null hypothesis we will accept the alternate hypothesis that, through the use of the Steprite device, not only will patients achieve overall clinical outcomes faster but there will be an associated decrease in cost burden to the medical system and the differences observed will be statistically significant as compared to rehabilitation of patients not using the Steprite device.

Patients who use the device post-surgery will demonstrate superior short-term improvements (i.e. 3 months post-surgery) with respect to self-reported functional outcomes and gait parameters, compared to a control group not using the device. The patients will self-report through the use of validated survey instruments including the KOOS survey (knee injury and osteoarthritis outcome score), LEFS (lower extremity functional scale) and/or KSS (knee society score), the latter of which includes a section for surgeon evaluation of patient functionality post operatively.

Study Design and Methods

This is a point of care clinical trial; a trial that functions to integrate research within a clinical setting that has the ability to readily deliver either modality of the proposal. This type of study design relies on provider referral of patients to be approached for consent, after which randomization to one of two treatment groups is facilitated; a control group of 15 patients participating in conventional rehabilitation regimens and an experimental group of 15 patients who will participate in the same rehabilitation regimen but facilitated

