through the use of Steprite. Importantly, care for patients is delivered as part of current adopted standards utilizing outcome measurements, the use of which and the interpretation of which is already built into care provided by the clinical facility, thereby negating the need to develop additional outcome measures. Recruitment of 30 patients will come from the investigators' normal patient population, among patients who are scheduled for partial or total knee arthroplasty. As there is no change in post op care for these patients from the investigators standard protocols other than monitoring and enforcement of home protocols, the same therapists involved in investigators' normal patient care will be involved with both arms of the study.

For this study, 30 patients represents a sample size deemed acceptable as a starting point. There are no other published studies using Steprite in comparative design trials. Determinations of sample size needed for this study, using 80% power and significance of 0.05, incorporate the use of a time frame in days or weeks for completion of the rehabilitation protocols that would allow for the detection of clinically significant differences between the group using Steprite and those using conventional therapies only. Given that conventional therapies can include skilled nursing, home health and outpatient visits and given that the need for each of these is highly variable dependent on the patient, it is difficult to assign a time value for determinations of sample size.

With that, a sample size of 30 participants divided into two groups represents an initial starting point, with the potential of incremental addition of more patients in order to achieve significance between the two study groups.

Statistical significance will be evaluated utilizing a standard t-test for two group comparison.

In preparation for the study, MedHab Inc. will at their expense train all involved investigators and therapists in the fitting and use of the StepRite device. Medhab will also train a lead therapist designated by the lead investigator to be in charge of overseeing and monitoring, ensuring proper use of the device. There is no cost to the patient, hospital or other funding entity for participation in this study. Medhab LLC will assume all costs associated with the training, application, device and use of the StepRite product for the full course of this study.

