Subjects for this study will be recruited from the patient population seen by the investigators during the normal course of business. There will be no outside recruitment of individuals or advertising as to the presence or use of the monitoring device to entice new patient referral. Prospective candidates will be asked by the lead investigator at the time they are designated surgical candidates. All documentation related to the study will be reviewed with the patient by the lead physician or his designee who is appropriately trained in discussing patient recruitment. Final decision and randomization to control or StepRite use will be done as part of the preoperative checkup just prior to surgery where both operative consent and study consent are discussed and signed.

Randomization:

Once a patient agrees to the study they would be sequentially randomized into whether or not they receive StepRite. The patients will be randomized to every other eligible patient gets the intervention. (ie: 1,3,5,7,9... will get StepRite ; 2,4,6,8 will not get StepRite) 15 Intervention subjects will be recruited and 15 control subjects will be recruited with an extra 5 patients to account for attrition and withdrawals.

Schedule of events

The intervention group will receive the StepRite device with standard conventional care and the control group will receive standard conventional care only. Both groups will receive outpatient, home health, and /or 24 hour physical therapy treatment plans per their surgeon's standard of care. The control group will undergo the conventional outpatient treatment program to 8 weeks as normally prescribed by the lead investigator. This consists of a twice weekly outpatient appointment with a physical therapist and prescribed home exercise program (see attached physical therapy protocol).

The patients randomly selected to wear the StepRite inserts will be fitted and instructed along with the patient's designated care giver in their use including initial pre-op measurements prior to their surgical date so that data collection can begin on the 1st day of rehab after surgery

Those patients not selected to wear step rite will receive instructions preoperatively of their expected therapy regimen and receive their baseline functional evaluation of the knee

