Both groups will be given log sheets to record their activity at home and when seen by the physical therapist. These will be returned and collected by the therapist weekly and scanned into/ kept in the patient's medical record file. A paper copy will be kept in the coordinator's office, 4A144B with the consent forms and any other study documents.

Both groups will also have routine self-assessment questionnaires (appendices 3, 4 KOOS and KSS) and functional testing performed by the PI and PT during the patient's regular clinic visit as standard of care.

Outcome measurements performed just after surgery and at time of discharge from hospital and standard of care post-surgical clinic visits to 8 weeks will indicate if any patients are experiencing unexpected delays in progress. Subjects will be visited at home by the Home Health therapists, and will visit and receive telephone consultations with the outpatient therapists, who will be able to monitor the patients' conditions and intervene if there are any problems related to the use of the device. The StepRite device will provide the therapist with more information about the patients' activity levels and progress than would usually be available to them and so is not expected to have any safety implications. The device and App. will prompt the patient with voice and text to complete their exercises as they are needed, while collecting data.

Device Flow Chart: standard of care post-op

The research coordinator will consent the patient prior to the surgery

The research coordinator will document the following information for the device on the device data collection form. (See attached)

- a. Name of patient
- b. Email of patient
- c. Phone number of patient
- d. Surgery date
- e. Expected date of discharge

The patient's information will then be entered into the steprite™ system and a patient account will be created by the Research Coordinator

Physical therapy will schedule the study protocol via the steprite™ system and enter the physical therapy start date as day after discharge.

MedHab™ sponsor ([name]) will contact the patient for the patient account set up and to obtain the following signatures required by MedHab (see attached)

- a. HIPAA
- b. Assignment of Benefits

MedHab™ will help the patient load the app, provide an overview of the app, and forward a tutorial video
MedHab™ will send the steprite™ device to the study Research Coordinator at TTUHSC

TTUHSC Orthopaedic Surgery

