Clinical Trials Coordinator, [name]

[name]

(t)[contact] (f)[contact]

The Research coordinator will fit the patient with the device, pair, and connect the device at time of discharge.

Patient will leave the hospital with the steprite™ device and instructions to charge device overnight for use the next day.

Patient will begin exercise regimen prompted by the StepRite App on the cell phone.

Physical therapy will communicate with the patient per the therapy protocol

Physical therapy is to work with patient per standard of care protocol with the addition of 3 patient outcome surveys, (KOOS, KSS, and the Lower Extremity functional scale) (see attached) at 4, 6, and 8 weeks post op, and the PI will see the patient as standard of care at visits 2, 6, and 12 weeks post-op. The 2 week patient outcome surveys will be completed at the 2 week standard clinic visit with the assistance of the study coordinator. All documents and data collection forms from physical therapy and clinic will be

scanned into the patients chart for review and kept in a locked file cabinet in the research coordinators office 4A144B.

Physical therapy advises the PI and MedHab two weeks prior to close of therapy on close out or extension procedure if needed.

The PI and MedHab extends the therapy or communicates the close out procedure with the patient.

Control Subject flow

The control group will have all Post-op standard of care as the device group without the use of the device.

Device Information

The device to be used in the study is the StepRite, manufactured and supplied by Medhab LLC. The device is considered exempt from IDE regulations, as it is a diagnostic device. It has been approved as a Class I medical device by the FDA.

The StepRite device consists of a thin insole which is placed inside the shoe.

The insole contains pressure sensors which record pressure data when exercises are performed, and contains an accelerometer, which records acceleration of the foot and is used to calculate velocity and activity levels.

A wireless connection between the insole and a cell phone application allows transfer of data.

The cell phone application will be supplied.

The cell phone application displays real-time feedback of pressure distributions to the user, and connects wirelessly to the Medhab servers to upload data onto the secure web interface, for access by the physical therapist or physician.

The device does not impart energy to the user.

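### The device-arm flow names the manufacturer and sponsor with the investigator in extending therapy; a minor safeguard should reserve that decision to clinicians in both arms

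*Combined protocol and SAP*

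**What the plan says.** The section Device Flow Chart: standard of care post-op lists the steps for StepRite patients. Its last two are "Physical therapy advises the PI and MedHab two weeks prior to close of therapy on close out or extension procedure if needed" and then "The PI and MedHab extends the therapy or communicates the close out procedure with the patient". The same section calls MedHab the sponsor, and Device Information names it as manufacturer and supplier.

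For controls, Control Subject flow says only "The control group will have all Post-op standard of care as the device group without the use of the device". Schedule of events adds "The control group will undergo the conventional outpatient treatment program to 8 weeks as normally prescribed by the lead investigator". Neither gives MedHab a part in a control patient's therapy.

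Objectives includes "To compare the overall cost of post-operative rehabilitation of patients involved in traditionally employed regimens versus those using the StepRite device", and Hypothesis and specific aims makes cost the second null hypothesis. Data Collection and Monitoring has cost gathered for each patient's whole rehabilitation. MedHab approaches the hospital and therapy departments for the figures, which then go to the lead investigator for analysis.

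**The concern.** A company with an interest in the result should not share in a treatment decision in one arm of a comparison, least of all when treatment length may feed an outcome. The protocol makes that link itself. Significance of this study lists among the drivers of cost "the need to protract the time required to attain clinical outcomes, where either or both in combination can increase rehabilitation expenditures". Study Design and Methods says that sample size determinations "incorporate the use of a time frame in days or weeks for completion of the rehabilitation protocols", although it assigns no value.

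If *therapy* in the extension step means the rehabilitation programme, the step bears on both quantities. Allocation is evident to everyone who handles the device. A reader of the cost result could not tell from the protocol whether the manufacturer had a say in how long device patients were treated.

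**Working it through.** No stated figure bears on this point and no arithmetic applies. The check is a comparison of texts.

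1. **Who acts in the extension step.** Physical therapy advises the investigator and MedHab. Both are then the subject of the verb *extends*. On its wording, the step gives MedHab a part in extension. It does not let MedHab act alone or overrule the clinicians.

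2. **Which arm it applies to.** The step stands in the device flow only. The control flow is defined by reference to the device group's standard care, so extension led by the investigator is open to controls as well. What has no control counterpart is MedHab's part.

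3. **What *therapy* means here.** Two readings are possible.
   - *StepRite programme only.* MedHab's other steps in the flow are setting up the account, obtaining signatures, helping with the app and shipping the device. Physical therapy schedules the protocol in the StepRite system and is told to "enter the physical therapy start date as day after discharge". A closing step for that schedule would fit the sequence.
   - *Rehabilitation itself.* The date entered in StepRite is called the physical therapy start date. Study Design and Methods describes the device arm as receiving the control regimen delivered with the help of StepRite, so the two schedules are not cleanly separate. The investigator's inclusion also makes a purely administrative reading uncertain.

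4. **Whether another section settles it.**
   - Study Design and Methods says post-operative care is unchanged apart from monitoring and reinforcing home exercise.
   - Schedule of events puts treatment plans in both groups under the surgeon's usual practice.
   - Risks says the only alteration may be less travel and fewer outpatient visits, depending on what the therapist observes.

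   All three favour the first reading. None addresses extension or limits MedHab's part in it.

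5. **What follows for the cost comparison.** On the first reading the effect is zero. On the second it is zero if MedHab's part changes no decision. Otherwise it depends on how many patients are affected, by how long and in which direction, and the documents give none of these.

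**The case against.** The strongest reply is that this is one loosely worded logistics sentence. It should be read with the general statements that care follows the surgeon and therapist, and with the steps around it, which are StepRite administration. The physical therapy protocol that Schedule of events calls attached is not in the available text and may contain extension or discharge criteria. Both arms keep activity logs that are collected weekly, and full cost is requested, so longer therapy should largely be visible. Most of this stands, and it is why the point is minor. What remains is that no available sentence confines MedHab to account handling when therapy is extended, and no described record captures the reason for an extension.

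Two stronger readings are tempting, and the documents support neither.

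- *The device arm has no end date while controls stop at 8 weeks.* A reader might infer this because the 8 weeks is stated for controls. Study Design and Methods gives device patients the same regimen, and the device flow schedules physical therapy surveys at 4, 6 and 8 weeks. A difference in planned length is not established.
- *MedHab can steer the cost result in its favour.* The text gives it no stated power to refuse or shorten therapy, and physical therapy starts the step. Extending billed rehabilitation would tend to raise device-arm cost, against the company's interest in that comparison. A gain for MedHab needs a further assumption, such as blocked extensions or better scores after longer therapy.

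**Conclusion.** The point holds as a minor conflict-of-interest safeguard. As worded, the device flow includes the manufacturer and sponsor, jointly with the investigator, in extending therapy. Controls have no counterpart, and rehabilitation cost is an objective. The text shows an opportunity for influence and does not show that influence occurs.

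No size or direction can be given. Any percentage would rest wholly on assumed numbers of patients and weeks, so none is offered. The conclusion assumes that staff may follow the flow chart as written, and that nothing in the attached physical therapy protocol already reserves extension to clinicians. If either assumption fails, or if only the StepRite account was meant, the matter is one of wording alone.

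**What to change.** Replace the last two steps of the device flow, and add the same rule to Control Subject flow, with wording such as: *In both groups the investigator and treating therapist alone decide whether rehabilitation is extended or closed, using the same clinical standard. In the device group MedHab is informed of the decision so that it can manage the StepRite account.*

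Record the therapy end date and the reason for any extension for every patient in both arms, and report them by arm beside the cost result.

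The cost is two sentences of protocol text and one short field per patient, for the 30 planned or at most the 35 requested. It needs no extra visits or staff, and sample size and analysis are unchanged. If account handling was all that was meant, the rewording of the step leaves conduct as it is and removes the ambiguity.

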The patient or designated care giver will be responsible for placing the insoles on their charging platform nightly.

Indicate the number of patients/charts/surveys/specimens needed.

The total number of patients needed in this study is 30, we will request a total of 35 to account for possible Attrition or withdrawals. 15 will be fitted with the StepRite device and 15 will follow the normal postoperative protocol without the device and be considered control subjects.

Inclusion criteria

Unilateral Partial or Total knee arthroplasty.

Age 45-75 yr. old

BMI <35

Access to Wi-Fi

Have appropriate smart phone and knowledge of use

Be willing to place StepRite app on their personal phone

Exclusion criteria

History of neuromuscular disorder (e.g. Parkinson's, Polio, or stroke).

Pregnancy

History of cognitive disease that would preclude ability to navigate smart phone

Method of identifying and recruiting subjects.

Recruitment will come from the investigators normal patient population who are scheduled for a partial or total knee replacement. The Investigators will identify and consult the research coordinator to assess eligibility.

Compensation given to subjects.

There will be no compensation given to subjects. They will be allowed to keep the insoles and access the app for at home therapy at no cost to them for as long as the device works.

Describe the site(s) where study will be done.

The main clinical/surgical portion of the study will take place at Texas Tech University Health Sciences Center department of Orthopaedic Surgery and University Medical Center Lubbock. The physical therapy departments used for this study will be the investigators preferences and standard of care, therefore they would be used if not on the study and are not study specific.

MedHab LLC (StepRite) will be collecting data from several sites to compare outcomes and cost. The secondary sites utilizing this device and doing similar studies are Covenant with [name] as the lead investigator, the Lubbock Heart Hospital with [name] as the lead investigator, and Texas Health Resources with [name] as lead investigator. All the secondary sites will use their standard of care preferences for clinical/surgical and physical therapy. TTUHSC will not be collecting data nor in any way be affiliated with the secondary study sites. They will acquire their local IRB approval for each site separately using similar device protocols.

Risks

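### Partial and total knee replacements are pooled, allocated without regard to procedure and compared by a plain t-test; adding procedure type as a model term is a low-cost gain in precision

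*Combined protocol and SAP*

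**What the plan says.** The Inclusion criteria admit "Unilateral Partial or Total knee arthroplasty", with no cap on either operation. The Objectives frame one comparison for both, "after partial or primary total knee replacement using validated survey tools to evaluate patient progress". The study title names only total knee arthroplasty, and no section says how the mix will be handled.

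Study Design and Methods sets "a control group of 15 patients participating in conventional rehabilitation regimens and an experimental group of 15 patients". The section on the number of patients adds "we will request a total of 35 to account for possible Attrition or withdrawals".

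Under Randomization, "The patients will be randomized to every other eligible patient gets the intervention": odd-numbered patients receive the device and even-numbered patients do not, along one sequence. No strata are mentioned.

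Study Design and Methods gives the analysis in one sentence: "Statistical significance will be evaluated utilizing a standard t-test for two group comparison". No covariate, stratum or subgroup appears there, or in Data Collection and Monitoring, where the cost comparison is described.

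Patients are recruited once they are scheduled for one operation or the other, and allocation takes place at the preoperative checkup. The scheduled procedure is therefore on record before the arm is assigned.

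**The concern.** If the two operations differ in recovery or in rehabilitation use, procedure type is a prognostic factor that is known in advance and costs nothing to collect. The plan leaves it out of both allocation and analysis. Two things follow.

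- Variation between procedures stays in the residual, so the comparison is less precise than it could be.
- With 15 per arm, the arms may receive noticeably different numbers of partial knees. A reader of the one result that this trial produces could then not tell how much of a difference in function or cost reflects the device and how much the mix of operations.

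The protocol itself says that the need for skilled nursing, home health and outpatient visits varies greatly between patients, and gives this as its reason for not sizing the trial. That makes it harder to justify leaving a measured candidate source of variation unused.

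**Working it through.** **Inputs from the documents.** 15 per arm, 30 in total, 35 requested; 80% power and a significance level of 0.05; two-group t-test; alternation.

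**Inputs assumed.** The documents give no share of partial knees and no difference between procedures on any outcome. I take 4 to 12 partial knees among 30 for the imbalance, shares of 10% to 40% for the variance, and a procedure difference *d* of 0.3, 0.5 or 0.8 within-procedure SD.

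**1. The plan's own figure.** The sample size of 30 cannot be reproduced. The protocol refers to "using 80% power and significance of 0.05" but gives no effect or SD, and says that "it is difficult to assign a time value for determinations of sample size". Solving the other way, 15 per arm with a two-sided t-test detects 1.06 SD. The attrition figure is consistent: 30 / (1 − 5/35) = 35.

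**2. Chance of an uneven mix.** Suppose the order of arrival is unrelated to procedure. With *m* partial knees among 30, the number in one arm of 15 is then hypergeometric, and the gap between arms is |2a − m|, where *a* is that number.

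| Partial knees *m* | P(gap ≥ 3) | P(gap ≥ 4) |
|---|---|---|
| 4 | 0.100 | 0.100 |
| 5 | 0.330 | 0.042 |
| 6 | 0.169 | 0.169 |
| 9 | 0.427 | 0.109 |
| 11 | 0.450 | 0.128 |
| 12 | 0.264 | 0.264 |

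The two extremes by hand:
- *m* = 4: 2 × C(15,4) / C(30,4) = 2 × 1365 / 27405 = 0.100.
- *m* = 11: 1 − 2 × C(15,5) × C(15,6) / C(30,11) = 1 − 2 × 3003 × 5005 / 54627300 = 0.450.

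The gap has the same parity as *m*. For odd *m*, a gap of 4 cannot occur and the last column is the chance of 5 or more. For even *m*, the two columns coincide. The rise and fall down a column is this parity effect, not a real trend in risk.

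**3. Size of the shift.** Shift = (gap / 15) × *d*. The standard error of the arm difference is √(2/15) = 0.365 SD. For a gap of 4:
- *d* = 0.3: 4/15 × 0.3 = 0.08 SD, or 0.22 SE.
- *d* = 0.5: 4/15 × 0.5 = 0.13 SD, or 0.37 SE.
- *d* = 0.8: 4/15 × 0.8 = 0.21 SD, or 0.58 SE.

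**4. Variance removed by adjustment.** With share *p*, the fraction is p(1 − p)d² / [1 + p(1 − p)d²].
- *p* = 0.1, *d* = 0.3: 0.0081 / 1.0081 = 0.8%.
- *p* = 0.4, *d* = 0.8: 0.1536 / 1.1536 = 13.3%.

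**5. Error rate and power by simulation** (40,000 trials per scenario, 15 per arm, shares of 10%, 30% and 50%, *d* of 0.5 and 1.0, random allocation).
- The overall type I error of the unadjusted t-test is 0.047 to 0.051.
- Among trials with a gap of 4 or more, it is 6.2% to 6.6% at *d* = 0.5 and about 10% at *d* = 1.0.
- For a device effect of 1.06 SD, adjusted power is 0.78 to 0.79 throughout. Unadjusted power is also 0.78 to 0.79 at *d* = 0.5; at *d* = 1.0 it is 0.77, 0.72 and 0.71 for the three shares.

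**6. Cost.** No mean, SD or difference by procedure is given for cost, so no shift can be computed.

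**The case against.** A reader might infer that leaving procedure out biases the trial or inflates its false-positive rate. The documents do not support that as a consequence of chance imbalance. Under random allocation the imbalance is part of sampling error, the t-test's standard error already covers it, and the simulated overall error stays near 5%. The distortion is conditional: it affects the trials in which the mix comes out uneven. This part of the objection stands.

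A reader might also take a serious imbalance as likely. That depends on a share that the protocol does not state. The title names only total knee arthroplasty, so partial knees may be few; with 3 among 30 a gap of 4 is impossible. Nor do the documents show that procedure predicts outcome or cost, or that it does so better than baseline score, age or BMI. The protocol describes one rehabilitation course for both operations and attributes variable use of care to the patient, not to the operation. At a difference of 0.3 SD the shift is minor, and at 0.5 SD adjustment brings almost no gain in power. All of this stands, and it limits how much weight the point can carry.

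Finally, it may be said that the larger weakness is alternation itself: the next assignment is predictable, and allocation falls at the visit where consent is signed. That is correct, and it is a separate issue. Selection could skew the procedure mix beyond chance, and adjusting for procedure would repair that one factor and no other.

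None of this defends ignoring a factor that is already recorded, when using it costs one degree of freedom.

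**Conclusion.** The point holds as a low-cost improvement. The pooling, the single alternating sequence, the unadjusted t-test and the prior knowledge of procedure type are all in the current text. What the plan gives up is some precision and protection against imbalance in this one factor: roughly 1% to 13% of outcome variance, and a possible shift of up to about 0.6 SE when the arms differ by 4 partial knees.

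These sizes rest on assumed shares and procedure differences, and the imbalance probabilities further assume that alternation acts as random. Whether cost is affected at all is unknown from the documents. The point does not alter the main limit of the design, a detectable difference of about 1.06 SD with 15 per arm.

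**What to change.** Replace the plain t-test with a prespecified linear model that has arm and procedure type (partial or total, as scheduled at allocation) as terms, for each clinical outcome and for the cost comparison. Write this into Study Design and Methods before any outcome data are compared by arm. The cost is one degree of freedom and one sentence of protocol text; eligibility, treatment and visits do not change.

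If alternation is replaced by concealed random allocation for its own reasons, stratify the block lists by procedure. That means two lists instead of one, and possibly an incomplete block in the smaller stratum. If allocation stays as it is, make the covariate adjustment anyway, but do not present it as a remedy for selection arising from a predictable sequence.
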